11.4.4.2 Definition of serious adverse event

An SAE is any untoward medical occurrence that at any dose:

- results in death,
- is life-threatening,

NOTE: The term "life-threatening" in the definition of "serious" refers to an event in which the patient was at risk of death at the time of the event; it does not refer to an event which hypothetically might have caused death if it were more severe.

- requires inpatient hospitalization or prolongation of existing hospitalization,
- results in persistent or significant disability/incapacity, or
- is a congenital anomaly/birth defect.

Medical and scientific judgement should be exercised in deciding whether expedited reporting is appropriate in various situations. These situations may include "important medical events" that, while not immediately life-threatening or resulting in death or hospitalization could jeopardize the subject's well-being or require intervention to prevent any of the other outcomes listed in the definition above. These should also usually be considered serious.

Examples of such events are intensive treatment in an emergency room or at home for allergic bronchospasm; blood dyscrasias or convulsions that do not result in hospitalization; or development of drug dependency or drug abuse.

11.4.4.3 Time period and frequency for collecting adverse events

All AEs (including SAEs) will be collected from the start of first IP administration until the last visit (Visit 12).

Any AE with start date on the day of each IP administration must be recorded with start time.

On the last treatment visit, information on new AEs or SAEs, if any, and stop dates for ongoing events must be recorded as applicable.

Investigators will not be obliged to actively seek AEs or SAEs after conclusion of the study participation. However, if the Investigator learns of any SAE, including a death, at any time after a participant has been discharged from the study, and they consider the event to be reasonably related to the study intervention or study participation, the Investigator must promptly notify the Sponsor.

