7.2 Secondary objectives

- 1. To compare the *in vivo* extracted amount (mg/unit) and extracted fraction (%) of nicotine between the unflavored NP 3 mg and 6 mg products and the comparator product, Longhorn Natural 18 mg.
- 2. To compare the PK profile between the unflavored NP 3 mg and 6 mg products and the comparator product, Longhorn Natural 18 mg.
- 3. To assess the PD effects, measured as pulse rate and subjective outcome measures, of the unflavored NP 3 mg and 6 mg products and the comparator product, Longhorn Natural 18 mg.
- 4. To compare the *in vivo* extracted amount (mg/unit) and extracted fraction (%) of nicotine between the unflavored NP 6 mg product and the flavored NP 6 mg products.
- 5. To compare the PK profile between the unflavored NP 6 mg product and the flavored NP 6 mg products.
- 6. To assess the PD effects, measured as pulse rate and subjective outcome measures, of the unflavored NP 6 mg products and the flavored NP 6 mg products.
- 7. To evaluate the safety and tolerability of new format NP products by administering single doses of unflavored and flavored NP products and the comparator product, Longhorn Natural 18 mg, in current, daily oral tobacco/nicotine pouch users.

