Subjects shall abstain from tobacco/nicotine products as well as smoking (cigarettes or ecigarettes) for 12 hours prior to each treatment visit (Visits 2-12). All treatment sessions will be performed during the morning hours (08:00 to 12:00) to facilitate abstinence.

The IPs will be administered as single pouches in a pre-determined randomized order. Subjects will keep the pouch still between the upper lip and gum for 30 minutes and will be instructed not to manipulate the pouch with the tongue or lips. They will also be instructed not

CONFIDENTIAL 25(64)

to eat, drink, chew gum, or brush their teeth for 30 minutes before, during, or 30 minutes after IP administration.

After 30 minutes, each used pouch will be collected and frozen (-20°C) pending analysis of residual nicotine content. Unused pouches from the same batch will serve as references and will be stored at -20°C pending analyses.

Blood samples for the assessment of nicotine plasma levels and PK parameters will be collected at pre-defined time points from pre-administration to 6 hours after each IP administration. The PD effects of the IPs will be determined using pulse rate measurements and subjective parameters (using VAS questions) at the same pre-defined time points as well as a MCQ 30 minutes after IP administration.

AEs will be collected through subject interviews and will also include any AEs reported spontaneously by the subjects, starting from the initiation of IP administration (Visit 2), and continuing until the last treatment visit (Visit 12). An overall schedule of event is presented in Table 8.1-1 and a detailed schedule of events for each treatment visit is presented in Table 8.1-2. Study assessments are described in Section 11.

CONFIDENTIAL 26(64)

Table 8.1-1 Schedule of events

Events	CSP section	Visit 1 Screening	Visit 2 First treatment visit	Visits 3-12 Treatment visits
Informed consent	11.2.1	X		
Demographics	11.2.2	X		
Medical/surgical history	11.2.3	X		
History of nicotine use	11.2.4	X		
Inclusion/exclusion criteria	9.4/9.5	X	X ¹	
Weight, height, and BMI	11.2.6	X		
Physical examination	11.2.7	X		
Vital signs (blood pressure and pulse rate)	11.2.8	X		
Electrocardiogram	11.2.9	X		
HIV, Hepatitis B and C	11.2.10	X		
Product familiarization session	11.2.11	X		
Pregnancy test ²	11.2.12	X	X	X^3
Urine drug screen ⁴	11.2.13	X	X	
Alcohol screen ⁴	11.2.14	X	X	
Randomization	9.9		X	
IP (pouch) administration	10.5		X ⁵	X ⁵
PK blood sampling (plasma)	11.3.1		X ⁵	X ⁵

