9.4 Inclusion criteria

For inclusion in the study, the subjects must fulfil the following criteria:

- 1. Willing and able to give written informed consent for participation in the study.
- 2. Subjects who have used oral tobacco/nicotine products for ≥1 year, with a minimum daily consumption of 5 or more pouches who are willing and able to use both tobacco-based moist snuff and NPs with high nicotine content.
- 3. Healthy male or female subject aged 21 to 60 years, inclusive.
- 4. Medically healthy subject without abnormal clinically significant medical history, physical findings, vital signs, ECG, and hepatitis B/C and human immunodeficiency virus (HIV) results at the time of the screening visit, as judged by the Investigator.

CONFIDENTIAL 30(64)

- 5. Successful completion of the product familiarization session for the comparator product use is required before the first IP administration. The subject should be able to follow the instructions, tolerate the product, and not experience any adverse effects different from what is expected during typical smokeless pouch use in the training session.
- 6. **Female subjects of child-bearing potential** must practice abstinence from heterosexual intercourse (only allowed when this is the preferred and usual lifestyle of the subject) or must agree to use a highly effective method of contraception with a failure rate of <1 % to prevent pregnancy for the duration of the study.

The following are considered highly effective methods of contraception:

- combined (estrogen and progestogen containing) hormonal contraception associated with inhibition of ovulation (oral, intravaginal, transdermal),
- progestogen-only hormonal contraception associated with inhibition of ovulation (oral, injectable, implantable),
- intrauterine device or intrauterine hormone-releasing system.

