11.2.11 Product familiarization session

At the end of the screening visit, a familiarization session will be conducted with the comparator product (Longhorn 18 mg nicotine). Subjects will not be required to fast prior to this training session. Extensive experience indicate that snus/nicotine pouch users can assess the effects of nicotine exposure and their ability to tolerate snus/nicotine pouch products within 20 to 30 minutes of use. Subjects will use the product once and there will be a minimum of 20 minutes duration of product use from when the subject places it in their mouth until they remove it. Subjects who successfully complete this familiarization session, meaning they can tolerate the product without any adverse effects different from what is typical for smokeless pouch use, will be eligible to continue participating in the study.

Used pouches from the familiarization session will not be retained for residual nicotine analysis and should be disposed of in compliance with local regulations.

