11.2.15 Baseline symptoms

A baseline symptom is defined as an event that occurs between the subject's signing of the ICF until the administration of IP (*i.e.*, an event that occurs during the screening period). Such events are not AEs but will be recorded as baseline symptoms in the AE Log in the eCRF.

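### Every randomized subject uses the 18 mg comparator at screening, but AE and SAE collection starts only at Visit 2, so reactions to that use are logged as baseline symptoms, not AEs.

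*Protocol*

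**What the plan says.** **The exposure.** Under section 11.2.11, at the end of the screening visit "a familiarization session will be conducted with the comparator product (Longhorn 18 mg nicotine"), and "Subjects will use the product once and there will be a minimum of 20 minutes duration of product use". It is not optional. Criterion 5 in section 9.4 reads: "Successful completion of the product familiarization session for the comparator product use is required before the first IP administration". Table 10.1-1 lists the comparator in its IP column.

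**The AE window.** Section 11.4.4.3 states that AEs, SAEs among them, "will be collected from the start of first IP administration until the last visit (Visit 12"). Section 8.1 describes AE collection as "starting from the initiation of IP administration (Visit 2"). Table 8.1-1 agrees: at Visit 1 it marks baseline symptoms but not AEs.

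**Status of earlier events.** Section 11.2.15 covers the whole interval from consent to IP administration and says: "Such events are not AEs but will be recorded as baseline symptoms in the AE Log in the eCRF". It makes no exception for reactions to the familiarization pouch.

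**Use of the data.** Secondary objective 7 (section 7.2) begins: "To evaluate the safety and tolerability of new format NP products by administering single doses"; it also covers the comparator. Its endpoint consists of AEs only. Section 17.7.4 summarizes AEs and SAEs by IP. Section 17.3.1 uses the full analysis set for safety, which admits only subjects who were randomized and dosed.

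**The concern.** The protocol gives a study product and then rules that reactions to it are not AEs. That matters in two ways.

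The first is safety capture. The duties to record intensity, causality and outcome (sections 11.4.4.5 to 11.4.4.9) and to report within 24 hours (section 11.4.4.10) are written for AEs and SAEs. No section extends them to baseline symptoms. The screening use is also less controlled than the treatment visits: it has a minimum duration but no stated maximum, and the 12-hour nicotine abstinence in section 9.6.1 applies only to Visits 2 to 12.

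The second is the safety description. Reactions at screening do not enter the comparator's column in the AE tables. A subject excluded because of such a reaction is outside the safety set altogether. The comparator's AE rates at Visits 2 to 12 thus come from people already selected for tolerating that product, and no product-specific filter of this kind precedes the ten pouches.

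**Working it through.** **Step 1: follow one event through the text.** Suppose a subject reacts to the familiarization pouch at Visit 1.

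| Provision | Consequence for this event |
|---|---|
| Table 10.1-1 (comparator listed as an IP) | The use could be read as an IP administration |
| Sections 8.1 and 9.4, criterion 5 | The first IP administration comes later, at Visit 2 |
| Section 11.4.4.1 (AE definition) | An unfavorable sign or symptom associated in time with product use, so an AE |
| Section 11.4.4 | AEs are assessed against the comparator as well as the IPs |
| Section 11.4.4.3 | Before the collection window opens, so not collected as an AE or SAE |
| Section 11.2.15 | Not an AE; logged as a baseline symptom |
| Section 17.7.4 | No place in the by-IP AE summaries |
| Section 17.3.1 | If the subject is not randomized, outside the safety set |

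A site cannot satisfy all of these rows. The definition in section 11.4.4.1 and the assessment rule in section 11.4.4 point to an AE; sections 11.2.15 and 11.4.4.3 point away from one. The definition is worded for medicinal products, but the protocol applies it to the study products.

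**Step 2: count the comparator uses.** Inputs from sections 9.3 and 17.2 are about 66 screened, 36 randomized, 32 evaluable and 10% dropout.

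- The plan's own figure reproduces: 32 / (1 − 0.10) = 35.6, rounded up to 36 randomized.
- Planned uses inside the AE window: 36, one for each randomized subject.
- Uses outside the window, lower end: 36, because each randomized subject must have completed the session.
- Uses outside the window, upper end: about 66, if every screened subject reaches the session.

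Share outside = uses outside / (uses outside + uses inside):

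- Lower: 36 / (36 + 36) = 36/72 = 50%.
- Upper: 66 / (66 + 36) = 66/102 = about 65%.

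These are shares of planned uses. Dropout before the comparator visit would reduce the 36 inside the window and raise both shares somewhat.

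**Step 3: subjects who never reach the safety set.** 66 − 36 = 30, and 30/66 = about 45% of those screened. Any of these 30 who used the comparator lie outside both the AE window and the safety set. How many reach the session, and how many fail because of it, is not given.

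**The case against.** The strongest reply is that little is actually lost. The events still go into the AE log. Section 11.4.4.10 sends an automatic alert when the investigator classifies an eCRF event as serious and signs it off, and nothing says that baseline-symptom entries are blocked from this. Section 11.4.4.3 requires prompt notice of a related SAE learned of after discharge, which may reach a screen failure. Section 11.4.4.6 asks for a conservative approach when seriousness is in doubt. Handling details are left to a safety management plan that is not shown. Reasons for screening failure must be kept (sections 9.2 and 9.7), so intolerance counts may be recoverable.

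Much of this stands. A reader might infer that a serious reaction at screening has no reporting route. The documents do not support that; what is missing is a stated obligation. The after-discharge clause does not cover a subject still in screening, and the possibility of flagging an event is not a duty to do so.

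A reader might also infer that the comparator will look better tolerated than it is, to the disadvantage of the pouches. That is not shown. Objective 7 is evaluated descriptively, with no AE contrast or test. Criterion 5 removes subjects who cannot tolerate the product or who have effects unlike those of ordinary pouch use, so expected nicotine effects do not by themselves exclude anyone. The same selected subjects use all 11 products, and selection on tolerance of an 18 mg product may lower event rates on the pouches too.

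Finally, the familiarization use is not standardized: at least 20 minutes rather than a fixed 30, in the subject's usual manner. Keeping it out of the by-IP columns is defensible. That argues for separate reporting, not for denying these events AE status.

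**Conclusion.** The point holds as a contradiction within the protocol and a gap in safety capture. Reactions to a mandatory use of a study product are defined as non-AEs, against the protocol's own AE definition. They carry no stated requirement for intensity or causality assessment or 24-hour SAE reporting, and they are left out of the by-IP summaries. The unseen SAP could add a listing of baseline symptoms, but it could not open AE and SAE collection at screening, because the protocol fixes the start.

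The size is 36 to about 66 comparator uses outside AE collection, or 50% to at most about 65% of planned uses. The lower figure assumes that only randomized subjects reach the session. The upper figure assumes that all 66 screened subjects do, although the session is held last and some may fail before it; it is a ceiling and not an estimate. Neither figure measures bias. Selection for tolerance of the comparator is real, but its size and net direction in any between-product comparison of AEs are unknown.

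The change should be made. The case rests on the reporting gap and the conflicting sections, not on a presumed bias.

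**What to change.** Reconcile sections 8.1, 9.4 (criterion 5), 10.1, 11.2.15, 11.4.4.1 and 11.4.4.3, and Table 8.1-1, as follows:

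- Start AE and SAE recording, including the 24-hour SAE rule, when the familiarization pouch is placed at Visit 1.
- Limit baseline symptoms to events between consent and that moment.
- State whether the familiarization use counts as an IP administration, so that the phrase first IP administration has one meaning throughout.
- In section 17.7.4, report familiarization events for all exposed subjects, including those not randomized, with the number not continuing because of intolerance. Keep these apart from the standardized 30-minute comparator use and do not pool them with it.

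The cost is protocol and eCRF wording and one extra listing or table. Events are already entered in the AE log, so no visit or procedure is added, and the sample size and primary analysis are unaffected.

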11.4.4.4 Collection of adverse events

AEs identified using any of the following methods will be recorded:

- AEs spontaneously reported by the subject.
- AEs observed by the Investigator or medical personnel.
- AEs elicited based on non-leading questions from the Investigator or medical personnel.

11.4.4.5 Recording of adverse events

AEs must be recorded in the AE Log of the eCRF. The Investigator must provide information on the AE, preferably as a diagnosis or at least as signs and symptoms; start and end dates,

CONFIDENTIAL 42(64)

start and end time; intensity; causal relationship to IP and comparator, action taken, and outcome. If the AE is serious, this must be indicated in the eCRF.

AEs, including out-of-range clinically significant clinical safety laboratory values, must be recorded individually, except when considered manifestations of the same medical condition or disease state; in such cases, they must be recorded under a single diagnosis.

11.4.4.6 Assessment of seriousness

The Investigator must assess and document the seriousness (serious or non-serious) of each AE using the definitions in Section 11.4.4.2. If the event is assessed as serious it must be reported as an SAE by the Investigator to the Sponsor according to Section 11.4.4.10.

For the seriousness criteria of inpatient hospitalization or prolongation of existing hospitalization to be fulfilled, the AE requires at least an overnight admission (24 hours) or prolongs a hospitalization beyond the expected length of stay. Emergency room visits that do not result in admission to the hospital should be evaluated for one of the other serious outcomes.

Planned hospitalizations or surgical interventions for a condition that existed before the subject signed the ICF, and that did not change in intensity, are not SAEs.

If there is any doubt as to whether an AE meets the definition of an SAE, a conservative approach will be taken, and the AE will be reported as an SAE.

11.4.4.7 Assessment of intensity

The grading of the intensity of AEs will follow the common terminology criteria for adverse events (CTCAE) v5.0 [11]. Grade refers to the severity of the AE. The CTCAE displays Grades 1 through 5 with unique clinical descriptions of severity for each AE based on this general guideline.

The Investigator must assess the intensity of an AE using the following definitions, and record it in the AE Log of the eCRF:

- **Grade 1** Mild; asymptomatic or mild symptoms; clinical or diagnostic observations only; intervention not indicated.
- Grade 2 Moderate; minimal, local, or non-invasive intervention indicated; limiting age-appropriate instrumental activities of daily living (ADL)*.
- Grade 3 Severe or medically significant but not immediately life-threatening; hospitalization or prolongation of hospitalization indicated; disabling; limiting self- care ADL**.
- **Grade 4** Life-threatening consequences: urgent intervention indicated.
- **Grade 5** Death related to AE.
- *Instrumental ADL refers to preparing meals, shopping for groceries or clothes, using the telephone, managing money, *etc*.

**Self-care ADL refers to bathing, dressing, and undressing, feeding self, using the toilet, taking medications, and not bedridden.

CONFIDENTIAL 43(64)

11.4.4.8 Assessment of causal relationship

The Investigator must assess the causal relationship between an AE and the use of the IP and comparator using the definitions below. Each assessment should be recorded in the AE log of the eCRF.

Probable The event has a strong temporal relationship to the IP and comparator, or

recurs on re-challenge, and another etiology is unlikely or significantly less

likely.

Possible The event has a suggestive temporal relationship to the IP and comparator,

and an alternative etiology is equally or less likely.

Unlikely The event has no temporal relationship to the IP and comparator or is due

to underlying or concurrent illness or effect of another drug (i.e., there is no

causal relationship between the IP, and the event).

An AE is considered causally related to the use of the IP and comparator when the causality assessment is probable or possible.

11.4.4.9 Outcome of adverse event

The Investigator must assess the outcome of an AE using the definitions below and record it on the AE log of the eCRF.

Recovered/resolved The subject has recovered completely, and no symptoms remain.

Recovering/resolving The subject's condition is improving, but symptoms still remain.

Recovered/resolved with

sequelae

The subject has recovered, but some symptoms remain (e.g., the subject had a stroke and is functioning normally, but has some

motor impairment).

Not recovered/not

resolved

The subject's condition has not improved, and the symptoms are unchanged (e.g., atrial fibrillation has become chronic).

Fatal

Unknown

11.4.4.10 Reporting of serious adverse events

The Investigator must report SAEs within **24 hours** of awareness to the Sponsor or its designee, this includes both initial information and any subsequent relevant/significant follow up information to a previously reported SAE. The primary mechanism for reporting an SAE will be via the eCRF. When the Investigator classifies the event as "serious" in the eCRF, and signs off the event, an automatic e-mail alert is sent to the Sponsor or its designee, and any other pre-defined recipients.

The backup procedure for reporting an SAE in case the eCRF is unavailable, will be via the paper SAE form provided in the Investigator Site File (ISF). The Investigator must fill in the SAE form and send it Sponsor or its designee. The study site must notify the site Monitor via phone or e-mail about the submission of the SAE report. As soon as the site personnel have access to the eCRF, the SAE must be reported electronically as well. The completed, signed, and dated paper SAE form should, within 24 hours, be scanned and delivered via encrypted e-mail or secure file transfer to:

CONFIDENTIAL 44(64)

A copy of the SAE paper form must also be delivered via encrypted e-mail or secure file transfer to CTC at:

All available information regarding the SAE must be entered in the AE log for the specific subject, *i.e.*, AE term, intensity, causality, outcome, seriousness criteria, action taken with IP, a narrative including the Investigators rationale for the causality assessment.

The SAE report will be reviewed by the Sponsor or its designee to ensure that the report is valid. The Sponsor or its designee will acknowledge receipt of the SAE report to the reporting Investigator. For SAEs where important or relevant information is missing, follow-up queries to the site are raised promptly to keep the regulatory reporting timelines.

Sponsor will perform an independent assessment of causality, including a rationale for the assessment. The causality assessment given by the Investigator should not be downgraded by the Sponsor. If the Sponsor disagrees with the Investigator's causality assessment, the opinion of both the Investigator and the Sponsor should be provided with the report.

If any additional information or documentation (*e.g.*, autopsy report) on the SAE is required for Sponsor's assessment of the SAE, the Sponsor or its designee will request this information from the Investigator, and the Investigator is required to promptly respond to the request.

Any subsequent relevant/significant follow-up information to a previously reported SAE must be entered in the AE log for the specific subject. If the Investigator makes any changes to the assessment of the case *e.g.*, changes in seriousness, causality, or intensity, a justification for the change should be provided in the case narrative. If the SAE report in the eCRF is updated, a new automatic e-mail alert is sent to Sponsor or its designee.

Detailed information on the SAE handling will be described in a study specific safety management plan.

